PROTOCOL TITLE:

Improving adherence to evidence-based practice using an innovative and easy-to-use health IT solution

PRINCIPAL INVESTIGATOR:

[name]
 Department of Psychiatry and Behavioral Neurosciences
 [contact]
 [contact]

VERSION NUMBER/DATE:

V10. February 13, 2024

REVISION HISTORY

*This table should only be used during submission of a Modification application to the IRB.

Revision #	Version Date	Summary of Changes	Consent Change?
1	July 8, 2021	We will conduct 90-minute focus groups instead of 60-minute individual interviews for Aim 1, resulting in a change in sample size from 60 to 72 for this aim; we revised the STTR Protocol, STTR Aim 1 Interviews Verbal Consent form, and STTR Aim 1 Focus Group Recruitment Email to reflect these changes; we updated the Aim 1 interview for focus groups; we uploaded Aim 2 trial questionnaires as separate word documents; we renamed documents to include the version number.	Yes
2	August 24, 2021	In addition to audio recording the focus groups for Aim 1, we will also screen-record. We revised the STTR protocol and STTR Aim 1 Focus Group Verbal Consent form to reflect these changes.	Yes
3	December 10, 2021	We revised the protocol to include new focus group recruitment strategy	No
4	January 13, 2022	We revised the protocol to include additional focus group strategy. We uploaded STTR Aim 1 Facebook Info Card for Patient and STTR Aim 1 Focus Group Facebook Recruitment Ad for Facebook recruitment.	No

5	January 24, 2022	Revised protocol to increase provider sample size to 30 and patient sample size to 60 Revised the following consent forms to update sample sizes: STTR Aim 2 Patients Trial Consent, STTR Aim 2 Providers Trial Consent	Yes
6	July 18, 2022	Revised protocol to include the re-consent procedure if a study client changes therapists, include option for families to be able to opt out of audio recording their therapy sessions and the Assessment of Core CBT Skills (ACCS) to assess provider's CBT delivery; increase provider sample size to 40 and client referral request to 3; and update provider compensation to be sent after family enrollment. We revised the STTR Aim 2 Patients Trial Consent, STTR Aim 2 Providers Trial Consent to reflect these changes; we updated STTR Aim 2 Info card for Providers, STTR Aim 2 Provider Patient Referrals Email, and STTR Aim 2 Audio Recordings Upload Email; we uploaded Study Introduction Script and STTR Aim 2 Trial ACCS.	Yes

1.0 Study Summary

1.1

Study Title	Improving adherence to evidence-based practice using an innovative and easy-to-use health IT solution
Study Design	Randomized trial methodology with assessments
Primary Objective/Purpose	The purpose of this study is to expand Adhere.ly—a web-based platform to improve provider implementation and patient engagement in homework (i.e., between-session practice of skills learned during therapy) during mental health treatment—to include new features and therapeutic exercises for adult patients, develop a plan for its implementation and sustainment, and preliminarily evaluate it by conducting a feasibility Optimization, Effectiveness, and Implementation (OEI) Hybrid trial.
Secondary Objective(s)/Purposes	N/A
Research Intervention(s)	Therapy
ClinicalTrials.gov NCT #	In progress.
Study Population	Masters-level mental health providers; Treatment seeking adults with anxiety and/or depression
Sample Size	N=282 Aim 1 focus groups: n=24 patients, 24 providers, 24 administrators Aim 1 survey: n=100 providers Aim 2 trial: n=50 providers; 60 adult patients
Study Duration for individual subjects	Aim 1 focus groups: 90-minutes each Aim 1 survey: 15 minutes Aim 2 trial providers: 28 hours over 9 months Aim 2 trial patients: 17 hours over 3 months
Study Specific Abbreviations/Definitions	OEI=Optimization, Effectiveness, and Implementation I/S=Implementation/sustainment CBT=Cognitive Behavioral Therapy EBT=Evidence-Based Mental Health Treatment mCFIR=Modified Consolidated Framework for Implementation Research

2.0 Objectives

2.1

The purpose of this study is to expand Adhere.ly (<https://adhere.ly/>)—a web-based platform to improve provider implementation and patient engagement in homework (i.e., between-session practice of skills learned during therapy) during mental health treatment—to include new features and therapeutic exercises for adult patients, develop a plan for its implementation and sustainment, and preliminarily evaluate it by conducting a feasibility Optimization, Effectiveness, and Implementation (OEI) Hybrid trial.

Aim 1. Understand and prioritize key stakeholder goals, challenges, affordances, and constraints

We will use an exploratory sequential (qual→quant) mixed-methods design to conduct semi-structured focus groups (qual) with mental health patients, providers, and administrators and a survey (quant) with providers. We will conduct 4 focus groups per stakeholder group (patient, provider, administrator) and each focus group session will include up to 6 participants. We will enroll 100 providers to complete the survey. Analyses will inform the design of new Adhere.ly features and exercises and an implementation/sustainment (I/S) blueprint.

Aim 2. Optimize, preliminarily evaluate, and implement Adhere.ly in community practice settings

We will conduct a small-scale feasibility OEI Hybrid trial with 30 community mental health providers randomized to Cognitive Behavioral Therapy (CBT) alone (n=25) vs. CBT+Adhere.ly (n=25), and 60 treatment seeking and provider-referred adult patients with clinically elevated anxiety and/or depression (outcomes), which we will assess at baseline and 3-months post-baseline. We will assess homework use by providers and adherence of patients (targets) weekly via session audio recordings and patient-report. We will optimize new Adhere.ly features and exercises, and our I/S blueprint during the trial and assess implementation outcomes post-implementation.

2.2

This is a feasibility trial and is not powered for hypothesis testing.

3.0 Background

3.1

Homework is one of the most integral components of high-quality mental health treatment

Mental health disorders affect 1 in 6 youth and 1 in 5 adults in the U.S. and are associated with costly physical and behavioral health problems. The quality of services these patients receive *vs.* should receive is highly variable and characterized as a “quality chasm” by the IOM.¹ Homework, or between-session practice of skills learned during therapy, is one of the most integral, yet underutilized components of high-quality, evidence-based mental health treatments (EBTs) such as Cognitive Behavioral Therapy (CBT).^{2,3} Homework exercises are assigned by providers in-session and completed by patients between sessions with the goal of practicing therapeutic skills in the environment

where they will be needed most.⁴ Homework enables the generalization of skills and behaviors learned during therapy, facilitates treatment processes, provides continuity between sessions, allows providers to better grasp patients' learning, and strengthens that learning, leading to improved maintenance of treatment gains.⁴⁻⁶ Meta-analytic and systematic reviews have shown that homework use by providers and adherence by patients predict increased treatment engagement, decreased treatment dropout, and medium-to-large effects on improvement in clinical outcomes (Cohen's $d=.45\text{--}.77$).⁷⁻¹¹ Simply put, 68% vs. 32% of patients can be expected to improve when therapy involves homework.⁹

Innovative solutions are needed to address barriers to the implementation of homework

Despite its many benefits, homework is implemented with variable effectiveness in "real world" clinical settings. Only 68% of general mental health providers and ~55% of family providers report using homework "often" to "almost always".^{12,13} Providers report using homework in an average of 57% of sessions and only 25% of providers report using expert-recommended systematic procedures for implementing homework (i.e., specifying frequency, duration, and location; writing down homework assignments for patients).¹⁴ A national survey revealed that 93% of mental health providers estimate rates of patient adherence to homework to be low to moderate,¹² and studies generally report low to moderate rates of patients' homework adherence.^{15,16} There are many barriers to successful homework implementation. For example, many providers struggle to consistently develop, assign, and assess homework exercises with their patients, and many patients have difficulty remembering to practice skills in an correct and timely way that fosters adequate learning.¹²⁻²¹

Technology is ubiquitous and can address homework barriers, but more research is needed

Between 92-96% of adults aged 18-49 years own a smartphone and 99% own a cellphone.^{22,23} Many health IT resources are effective, practical, desired by patients and providers, and available at low cost.²⁴ Prior work by our team and others suggests that health IT solutions have tremendous potential to positively affect homework use and adherence and as a result, the quality of mental health treatment.^{21,25,26} Some existing health IT resources include features to support homework implementation (e.g., voice and SMS reminders and feedback, self-monitoring, assessment),^{25,26} and some *mHealth* apps with homework-specific resources have been developed with positive preliminary effects.²⁷⁻³³ However, these resources are generally age-, disorder-, and treatment protocol-specific, and solely native app- based with limited interaction between patient and provider interfaces. Further, more data are needed to ensure that these resources have the ability to target homework use by providers and adherence by patients and be implemented in community practice settings.

Adhere.ly can address homework barriers and limitations of existing health IT resources

To address these limitations, our team of experts at Adhere.ly, LLC, USF, and the Medical University of South Carolina (MUSC), and Doxy.me, LLC developed Adhere.ly,

an innovative, state-of-the-art, and user-friendly solution to improve provider implementation and patient engagement in homework during EBTs. Adhere.ly is a free web-based platform with optional provider login, patient management features, and built-in therapeutic exercises (e.g., self-monitoring, relaxation, cognitive coping, emotion regulation, exposure therapy) for providers to introduce, practice, and assign as homework to patients. Patients receive SMS or email reminders with links to practice those exercises during the week on the days/times specified by providers, and providers are able to review patients' homework adherence and relevant data (e.g., self-monitoring ratings) on their dashboard. Adhere.ly was developed as a resource to improve homework implementation by providers and adherence in children and caregivers during treatment for childhood PTSD (F32 MH108250; K23 MH118482; PI [name]). One of the objectives of this NIMH Phase I STTR project, conducted in partnership with Adhere.ly, LLC, is to expand Adhere.ly to include additional features (e.g., more guidance for providers in-session) and therapeutic exercises that support a range of youth **and adult** EBTs.

3.2

Perspectives on homework barriers and mHealth solutions (NIMH F32 MH108250)

Adhere.ly's initial conceptualization was informed by semi-structured qualitative interviews with 21 national trainers in Trauma Focused Cognitive Behavioral Therapy (TF-CBT)³⁴ and 15 youth/caregiver TF-CBT patients. These interviews explored potential *m*Health solutions to barriers to implementing homework during youth mental health treatment. Results suggested that many providers struggle to consistently develop, assign, and assess homework exercises with their patients, many of whom have difficulty remembering to practice skills in a correct and timely way that fosters adequate learning. Trainers and patients were generally positive about the potential for *m*Health to improve the implementation of homework and provided suggestions for *m*Health solutions in terms of functionality and user experience.²¹

Ongoing development and evaluation of Adhere.ly (NIMH K23 MH118482)

The current version of Adhere.ly was developed as a resource to improve homework implementation by providers and adherence in children and caregivers during treatment for childhood anxiety, depression, and PTSD. As such, the therapeutic exercises are mostly child focused.

Survey among community mental health providers

We recently conducted a survey among 277 community mental health providers who use telemedicine for about 25% of their caseload. The majority of respondents were master's (64%) and doctoral-level (25%) providers working in individual practice (70%) and small clinic (18%) settings. Most providers reported treating adults (98%) with anxiety (95%), depression (87%), and PTSD (77%), and using cognitive-behavioral (82%) and interpersonal (52%) treatment approaches in their general practice. Almost half (41%) of providers reported assigning homework "never" to "sometimes," and the most common exercises assigned were mindfulness (78%), coping/emotion regulation (73%), relaxation (70%), interpersonal skills (56%), self-monitoring (56%), problem-solving (54%), and cognitive flexibility/reappraisal (51%).³⁵

4.0 Study Intervention

4.1

We designed Adhere.ly as a simple, HIPAA compliant, web-based application to help mental health providers implement homework during CBT with patients with elevated PTSD, anxiety, and/or depression. The three major components of Adhere.ly help providers to (1) **Practice** interactive, digitized CBT exercises with patients in-session; (2) **Remind** patients to practice CBT exercises for homework, and (3) **Review** homework during the next session. These functions are accessible via tabs on the left side of the site, as displayed in Figure 1.

[figure not shown]

Figure 1

The **Practice** component includes several brief interactive, digitized CBT exercises for providers to practice with patients in-session within each of the following areas: relaxation, affect and emotion, cognitive coping, exposure, parent-child activities, enhancing safety, and parenting videos (Figures 2-4).

[figure not shown]

Figure 2

[figure not shown]

Figure 3

[figure not shown]

Figure 4

The **Remind** component enables providers to set automated text message/email reminders with editable default days/times, for patients to practice exercises between-session. This includes all exercises found in the **Practice** component as well as automated customizable reminders, encouraging messages, self-monitoring, and parenting exercises (Figures 5-6). Patients receive automated text message (or email) reminders during the following week on the specified days and times that contain links to the digitized exercises, which are opened and completed in the patients' smartphone or computer browser (i.e., no downloads or logins are required).

[figure not shown]

Figure 5

[figure not shown]

Figure 6

The **Review** component enables providers to view patients' homework completion and relevant data for certain exercises (e.g., self-monitoring ratings, anxiety ratings during exposure exercises; Figure 7).

[figure not shown]

Figure 7

Adhere.ly is accessed by computer, tablet, and/or smartphone browser so it does not require any downloads by patients or providers. Patients do not create accounts or log in, and providers who choose not to create an account are still able to use the site with limited functionality. This functionality is limited in that it does not allow providers to save patient contact information (i.e., it must be entered every time a reminder is scheduled), does not allow providers to review homework results, and limits reminders to customizable reminders, encouraging messages, and self-monitoring and relaxation exercises (Figure 8).

[figure not shown]

Figure 8

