5.0 Procedures Involved

5.1

Aim 1. Understand and prioritize key stakeholder goals, challenges, affordances, and constraints

Aim 1 of this study will use an exploratory sequential (qual→quant) mixed-methods design to conduct semi-structured focus groups (qual) with mental health patients, providers, and administrators and a survey (quant) with providers. We will conduct 4 focus groups per stakeholder group (patient, provider, administrator) and each focus group session will include up to 6 participants. Half of the focus groups will consist of stakeholders from public healthcare institutions and the other half will consist of stakeholders from private healthcare institutions. We then will enroll 100 providers to complete the survey. Analyses will inform the design of new Adhere.ly features and exercises and an implementation/sustainment (I/S) blueprint.

Aim 2. Optimize, preliminarily evaluate, and implement Adhere.ly in community practice settings

Aim 2 of this study will use a randomized controlled OEI Hybrid trial design. The trial will include 50 community mental health providers randomized within their respective practice locations to administer CBT+Adhere.ly (n=25) vs. CBT alone (n=25) to a total of 60 treatment-seeking adult mental health patients with clinically elevated anxiety and/or depression-referred and treated by providers. Study staff will conduct pre- and post- implementation assessments remotely with providers and will facilitate web-based administration of baseline and 3-month post-baseline assessments with patients via REDCap. Treatment sessions may be audio recorded and uploaded to REDCap by providers and coded by study staff to assess provider assignment and assessment of homework. Clients will have the option to allow providers to audio-record their therapy sessions through the consent. Patient homework adherence will be assessed weekly the day of their next session using a REDCap survey, a link to which will be sent via automated text-message and/or email reminders, or by telephone after 1 day of no response.

5.2

 Audio/Video Recording	 Psychophysiological Recording
 Behavioral Interventions	 Record Review - Educational
 Behavioral Observations and Experimentations	 Record Review - Employee

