 Deception	 Record Review- Medical
 Focus Groups	 Record Review - Other
 Interviews	 Specimen Collection or Analysis
 Investigational Device – Non-Significant Risk (e.g. Mobile Applications)	 Surveys and/or Questionnaires
 Psychometric Testing	 Other Social-Behavioral Procedures

Aim 1. Understand and prioritize key stakeholder goals, challenges, affordances, and constraints

Study staff will invite up to 24 adult mental health patients, 24 providers, and 24 administrators to participate in remote (i.e., video conference or telephone), ≤90-minute, screen and audio-recorded, semi-structured focus groups to inform the design of new Adhere.ly features and exercises and an I/S blueprint. Study staff will email and/or call mental health providers and administrators registered with Doxy.me—who will be asked to refer adult patients—with information about the study and an invitation to participate (see attached Letter of Support from [name] at Doxy.me). Study staff will also post recruitment flyer on Facebook and submit research study into the Institute of Translational Health Sciences (ITHS) to recruit adult patients. Study staff will schedule an appointment to obtain verbal informed consent and begin focus groups, which will include basic demographic questions, an overview and brief demonstration of Adhere.ly, and will utilize the Modified Consolidated Framework for Implementation Research (mCFIR) domains relevant to Adhere.ly features and exercises and this implementation (i.e., intervention characteristics, outer settings, inner settings, end-user characteristics, and process of implementation).^{36,37} Next, we will draw upon insights obtained from these focus groups and the literature on homework and processes-based CBT to develop a quantitative web-based survey that we will administer to 100 mental health providers, recruited via emails to providers registered with Doxy.me, to prioritize certain goals, challenges, features, and exercises.^{38,39}

Aim 2. Optimize, preliminarily evaluate, and implement Adhere.ly in community practice settings

Recruitment of providers

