We will leverage research-practice partnerships established in Aim 1 to recruit 50 master's-level mental health providers and will recruit additional providers via emails to mental health providers registered with doxy.me, if needed. Providers will be contacted by study staff via telephone and/or email to inform them about the study and inquire about their interest in participating. Providers who express interest in participating in the study will be scheduled for a 60-minute, televideo-based consent and training process with study staff to discuss the study, referral procedures, audio recording sessions, and uploading recordings to REDCap. Signed informed consent from providers will be obtained by study staff via REDCap e-Consent. Afterwards providers will complete a

demographics questionnaire and the Attitudes Toward Homework Questionnaire (ATHQ).¹²

Recruitment of patients

We will recruit 60 treatment-seeking adults over 18 with clinically elevated anxiety and/or depression. Patients will be referred and by providers following their initial intake session with that provider. We will ask providers to refer 3-4 patients to maximize the likelihood of treatment completion with at least 3 patients. Providers will receive automated weekly emails with reminders to make referrals and links to a REDCap referral form. Providers will also be able to provide referral information via telephone or email if preferred. If patients express interest in the study, providers will assist them in completing the referral or obtain verbal consent to submit their referral information.

Upon receiving a referral, study staff will contact patient within one working day to provide study information, assess eligibility, obtain signed informed consent from patients via REDCap e-Consent, and assist patient in completing baseline assessments. Study staff will assess eligibility by: (1) administering a phone screen to the patient; and (2) emailing or texting patient a link through the REDCap system to a survey that will include a brief demographic questionnaire, the Generalized Anxiety Disorder-7 (GAD-7) or Patient Health Questionnaire-8 (PHQ-8).⁴⁰⁻⁴² Patients who are eligible, as indicated by a score ≥ 10 on the GAD-7 or PHQ-8, will then provide informed consent via REDCap e-Consent, and complete the remaining study baseline questionnaires.

Treatment

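### CBT-alone providers can reach Adhere.ly by several routes, yet the protocol plans no measure of control-arm use, and use without an account may not be traceable

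*Combined protocol and SAP*

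**What the plan says.** **Access.** Section 3.1 states: "Adhere.ly is a free web-based platform with optional provider login". Section 4.1 adds that "providers who choose not to create an account are still able to use the site with limited functionality". Without an account a provider cannot store patient contacts or review homework results, and has only some of the reminder types.

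**Awareness.** Under section 5.2, Aim 1 focus groups (up to 24 providers and 24 administrators) include "an overview and brief demonstration of Adhere.ly". For Aim 2 the same section says: "We will leverage research-practice partnerships established in Aim 1 to recruit 50" providers, with doxy.me emails as a back-up. The eligibility criteria in 9.1 do not exclude Aim 1 participants or earlier users of the platform. Section 21.2 shows that the provider consent form mentions the CBT+Adhere.ly condition by name.

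**Allocation.** Section 5.1 has providers "randomized within their respective practice locations", 25 per arm, with 60 patients in total. Section 5.2 asks both arms to deliver CBT in their usual way.

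**Measurement.** Section 16.1 sets a benchmark of 70% of providers and patients using Adhere.ly, and Table 2 repeats use as a percentage; neither names an arm. Section 16.2 plans to download platform usage data with names and contact details and merge them into REDCap, without restricting this to one arm. Table 1 lists no measure of Adhere.ly use. Session recordings, which clients may decline, are coded with the HAACS and ACCS. Post-implementation interviews cover the CBT+Adhere.ly condition only.

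**The concern.** A control provider who knows the product, works beside intervention providers and needs no account could use it with study patients. As far as the protocol shows, this would breach nothing: controls are asked only to practise as usual. Such use would pull the between-arm comparisons in 16.1 (ANCOVA on clinical outcomes, ANOVA on homework use and adherence) towards no difference.

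The larger stake is Phase II. Whether providers within one practice can be kept apart, or whether practices must be randomised instead, is a question that a feasibility trial is well placed to answer. The plan does not set out to answer it.

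**Working it through.** The protocol states no contamination rate, target effect or power for Aim 2, so there is no design figure to reproduce. Four checks follow.

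**1. Which planned data could show control-arm use?**

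- *Control provider with an account:* could be found in the 16.2 download, if someone looks by arm.
- *Reminders sent without an account:* 4.1 says that patient contact details must be entered each time, so these might be matched to REDCap contacts. Whether they are logged is not stated.
- *In-session practice without an account:* no described record. A recording might capture it, but recordings are optional and no code for Adhere.ly use is described.
- *Direct report by provider or patient:* none described.

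**2. The 70% benchmark.** Inputs: 50 providers (25 per arm) and 60 patients (30 per arm if split evenly, an assumption).

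- Pooled reading: 0.70 × 50 = 35 providers and 0.70 × 60 = 42 patients. This exceeds those assigned to Adhere.ly by 35 − 25 = 10 providers and 42 − 30 = 12 patients. It could be met only through control-arm use, which would then count as success.
- CBT+Adhere.ly arm only: 0.70 × 25 = 17.5, so 18 providers, and 0.70 × 30 = 21 patients. This is attainable but says nothing about controls.

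Neither reading gives a control-arm rate.

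**3. Size of dilution (illustration).** Let c be the share of control patients who receive the full effect. The observed difference is (1 − c) times the true one. At fixed power, the sample size rises by 1/(1 − c)².

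| c (assumed) | Observed share of effect | Sample size multiplier |
|---|---|---|
| 10% | 0.90 | 1/0.81 = 1.23 |
| 20% | 0.80 | 1/0.64 = 1.56 |
| 30% | 0.70 | 1/0.49 = 2.04 |

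Outcome data could not reveal this. Section 3.1 cites d = 0.45 to 0.77 for homework in general, not for Adhere.ly. At c = 30% the loss is 0.30 × 0.45 = 0.135 to 0.30 × 0.77 = 0.231. The 95% half-width for d, 1.96 × √(2/n) with SD 1 and no clustering, is 0.51 at n = 30 per arm. At n = 21 (30 × the 70% retention benchmark) it is 0.60.

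**4. What direct measurement would give.** Exact (Clopper-Pearson) 95% intervals for the 25 control providers:

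| Users | Rate | 95% CI |
|---|---|---|
| 0 of 25 | 0% | 0 to 13.7% |
| 1 of 25 | 4% | 0.1 to 20.4% |
| 3 of 25 | 12% | 2.5 to 31.2% |
| 5 of 25 | 20% | 6.8 to 40.7% |

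**The case against.** A reader might infer that control-arm use goes wholly unmeasured and that any dilution would be invisible. The documents do not support that. The 16.2 download carries identifiers and is not limited by arm, so it could show account holders in the control arm and perhaps reminders matched on patient contacts. Nothing says that account-less activity is unlogged; it is simply not described.

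Other points on the same side also stand:

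- The items of the Provider Demographics Questionnaire, the operating procedures and the manual of procedures (16.3) are not shown. A question on prior use or an instruction to controls may exist there. The claim can only be that the protocol describes neither.
- The exposure routes are possibilities. The demonstration is stated for the focus groups, not for the 100-provider survey, and the overlap of individuals with Aim 2 is unknown. Section 3.2 calls the current exercises mostly child focused. In the earlier survey reported there, 70% of providers were in individual practice, and mixing within locations would matter little for such providers.
- Account-less use is a reduced version (4.1), so full-effect dilution overstates that route.
- Section 2.2 says: "This is a feasibility trial and is not powered for hypothesis testing", and 16.1 disclaims conclusions on effectiveness. With 25 control providers the measured rate would be imprecise: 3 of 25 is compatible with all of 10%, 20% and 30%.

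These points limit the consequence for this trial's own results. They do not supply a planned measure, an arm-specific denominator or a report of use by arm.

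**Conclusion.** The point holds in a limited form. The routes to control-arm use are in the text. The protocol describes no instruction to controls, no planned measure or analysis of their use, and no arm for the 70% benchmark or the Table 2 percentage. Part of any control-arm use could be recovered from the 16.2 download; account-less in-session use may not be.

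How much contamination will occur is unknown. The multipliers of 1.23, 1.56 and 2.04 are upper illustrations. They rest on assumed rates, on control users receiving the full effect, and on Phase II having the same contamination, which need not follow if practices were randomised. They should not be read as a forecast.

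This is an inexpensive improvement worth making, not a flaw that undermines the trial. The gain is a contamination estimate for Phase II: no users among 25 control providers would put the upper 95% limit at 13.7%.

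**What to change.** 1. In 16.1 and Table 2, define the 70% use benchmark on the CBT+Adhere.ly arm only.
2. In 16.2, state that the platform download will be searched for CBT-alone providers and their patients.
3. Add one item on prior Adhere.ly use to the provider baseline form, and one item on Adhere.ly use with study patients to both the provider follow-up and the patient 3-month survey, in both arms.
4. Tell CBT-alone providers that Adhere.ly belongs to the other arm. The only training session described comes with consent, and 5.2 withholds assignment until the first patient is enrolled, so the natural moment is when assignment is disclosed.
5. Report use by arm, with an exact confidence interval, as a feasibility outcome. Keep the between-arm analyses as randomised.

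The cost is three short items, one search of data already being collected, one sentence to controls and a protocol modification. For providers already enrolled, the baseline item comes too late, but the end-of-study items and the search still work. There are two downsides. The questions may draw controls' attention to Adhere.ly, which is a reason to ask only at baseline and at the end. The estimate from 25 control providers will also be wide, so it can inform the Phase II choice of randomisation unit but not settle it.
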